#### **7.4 USE OF COMPUTERIZED SYSTEMS**

When clinical observations are entered directly into an investigational site's computerized medical record system (i.e., in lieu of original hardcopy records), the electronic record can serve as the source document if the system has been validated in accordance with Health Authority requirements pertaining to computerized systems used in clinical research. An acceptable computerized data collection system allows preservation of the original entry of data. If original data are modified, the system should maintain a viewable audit trail that shows the original data as well as the reason for the change, name of the person making the change, and date of the change.

#### **7.5 RETENTION OF RECORDS**

Records and documents pertaining to the conduct of this study and the distribution of IMP, including eCRFs, Informed Consent Forms, laboratory test results, and medication inventory records, must be retained by the Principal Investigator for at least 15 years after completion or discontinuation of the study, or for the length of time required by relevant national or local Health Authorities, whichever is longer. After that period of time, the documents may be destroyed, subject to local regulations. No records may be disposed of without the written approval of the Sponsor. Written notification should be provided to the Sponsor prior to transferring any records to another party or moving them to another location.

### **8. ETHICAL CONSIDERATIONS**

#### **8.1 COMPLIANCE WITH LAWS AND REGULATIONS**

This study will be conducted in full conformance with the ICH E6 guideline for Good Clinical Practice and the principles of the Declaration of Helsinki, or the laws and regulations of the country in which the research is conducted, whichever affords the greater protection to the individual. The study will comply with the requirements of the ICH E2A guideline (Clinical Safety Data Management: Definitions and Standards for Expedited Reporting). Studies conducted in the United States or under a U.S. Investigational New Drug (IND) application will comply with U.S. FDA regulations and applicable local, state, and federal laws. Studies conducted in the EU/EEA will comply with the EU Clinical Trial Directive (2001/20/EC).

**RO7049389—F. Hoffmann-La Roche Ltd**  
68/Protocol YP39406, Version 4

## **8.2 INFORMED CONSENT**

The Sponsor's sample Informed Consent Form will be provided to the site. If applicable, it will be provided in a certified translation of the local language. The Sponsor or its designee must review and approve any proposed deviations from the Sponsor's sample Informed Consent Forms or any alternate consent forms proposed by the site (collectively, the "Consent Forms") before IRB/EC submission. The final IRB/EC-approved Consent Forms must be provided to the Sponsor for Health Authority submission purposes according to local requirements.

The Consent Forms must be signed and dated by the subject before his or her participation in the study. The case history or clinical records for each subject shall document the informed consent process and that written informed consent was obtained prior to participation in the study.

The Consent Forms should be revised whenever there are changes to study procedures or when new information becomes available that may affect the willingness of the subject to participate. The final revised IRB/EC-approved Consent Forms must be provided to the Sponsor for Health Authority submission purposes.

Subjects must be re-consented to the most current version of the Consent Forms (or to a significant new information/findings addendum in accordance with applicable laws and IRB/EC policy) during their participation in the study. For any updated or revised Consent Forms, the case history or clinical records for each subject shall document the informed consent process and that written informed consent was obtained using the updated/revised Consent Forms for continued participation in the study.

A copy of each signed Consent Form must be provided to the subject. All signed and dated Consent Forms must remain in each subject's study file or in the site file and must be available for verification by study monitors at any time.

## **8.3 INSTITUTIONAL REVIEW BOARD OR ETHICS COMMITTEE**

This protocol, the Informed Consent Forms, any information to be given to the subject, and relevant supporting information must be submitted to the IRB/EC by the Principal Investigator and reviewed and approved by the IRB/EC before the study is initiated. In addition, any subject recruitment materials must be approved by the IRB/EC.

The Principal Investigator is responsible for providing written summaries of the status of the study to the IRB/EC annually or more frequently in accordance with the requirements, policies, and procedures established by the IRB/EC. Investigators are also responsible for promptly informing the IRB/EC of any protocol amendments (see Section 9.5).

In addition to the requirements for reporting all adverse events to the Sponsor, investigators must comply with requirements for reporting serious adverse events to the local health authority and IRB/EC. Investigators may receive written IND safety reports

**RO7049389—F. Hoffmann-La Roche Ltd**  
69/Protocol YP39406, Version 4

or other safety-related communications from the Sponsor. Investigators are responsible for ensuring that such reports are reviewed and processed in accordance with Health Authority requirements and the policies and procedures established by their IRB/EC, and archived in the site's study file.

#### **8.4 CONFIDENTIALITY**

The Sponsor maintains confidentiality standards by coding each subject enrolled in the study through assignment of a unique subject identification number. This means that subject names are not included in data sets that are transmitted to any Sponsor location.

Subject medical information obtained by this study is confidential and may only be disclosed to third parties as permitted by the Informed Consent Form (or separate authorization for use and disclosure of personal health information) signed by the subject, unless permitted or required by law.

Medical information may be given to a subject's personal physician or other appropriate medical personnel responsible for the subject's welfare, for treatment purposes.

Data generated by this study must be available for inspection upon request by representatives of the U.S. FDA and other national and local Health Authorities, Sponsor monitors, representatives, and collaborators, and the IRB/EC for each study site, as appropriate.

#### **8.5 FINANCIAL DISCLOSURE**

Investigators will provide the Sponsor with sufficient, accurate financial information in accordance with local regulations to allow the Sponsor to submit complete and accurate financial certification or disclosure statements to the appropriate Health Authorities. Investigators are responsible for providing information on financial interests during the course of the study and for one year after completion of the study (i.e., LSLV).

### **9. STUDY DOCUMENTATION, MONITORING, AND ADMINISTRATION**

#### **9.1 STUDY DOCUMENTATION**

The Investigator must maintain adequate and accurate records to enable the conduct of the study to be fully documented, including but not limited to the protocol, protocol amendments, Informed Consent Forms, and documentation of IRB/EC and governmental approval. In addition, at the end of the study, the Investigator will receive the Subject data, which includes an audit trail containing a complete record of all changes to data.

#### **9.2 SITE INSPECTIONS**

Site visits will be conducted by the Sponsor or an authorized representative for inspection of study data, subjects' medical records, and eCRFs. The Investigator will

**RO7049389—F. Hoffmann-La Roche Ltd**

70/Protocol YP39406, Version 4

permit national and local Health Authorities, Sponsor monitors, representatives, and collaborators, and the IRBs/ECs to inspect facilities and records relevant to this study.

### **9.3 ADMINISTRATIVE STRUCTURE**

The Sponsor of the trial is F. Hoffmann-La Roche Ltd. The Sponsor is responsible for the study management, data management, statistical analysis and medical writing for the clinical study report.

### **9.4 PUBLICATION OF DATA AND PROTECTION OF TRADE SECRETS**

The results of this study may be published or presented at scientific meetings. If this is foreseen, the Investigator agrees to submit all manuscripts or abstracts to the Sponsor prior to submission. This allows the Sponsor to protect proprietary information and to provide comments based on information from other studies that may not yet be available to the Investigator.

The Sponsor will comply with the requirements for publication of study results. In accordance with standard editorial and ethical practice, the Sponsor will generally support publication of multicenter trials only in their entirety and not as individual center data. In this case, a coordinating Investigator will be designated by mutual agreement.

Any formal publication of the study in which contribution of Sponsor personnel exceeded that of conventional monitoring will be considered as a joint publication by the Investigator and the appropriate Sponsor personnel.

Authorship will be determined by mutual agreement and in line with International Committee of Medical Journal Editors authorship requirements

Any inventions and resulting patents, improvements, and/or know-how originating from the use of data from this study will become and remain the exclusive and unburdened property of the Sponsor, except where agreed otherwise.

### **9.5 PROTOCOL AMENDMENTS**

Any substantial protocol amendments will be prepared by the Sponsor. Substantial protocol amendments will be submitted to the IRB/EC and to regulatory authorities in accordance with local regulatory requirements.

Approval must be obtained from the IRB/EC and regulatory authorities (as locally required) before implementation of any changes, except for changes necessary to eliminate an immediate hazard to subjects or any non-substantial changes, as defined by regulatory requirements.

**RO7049389—F. Hoffmann-La Roche Ltd**  
71/Protocol YP39406, Version 4

**RO7049389—F. Hoffmann-La Roche Ltd**  
73/Protocol YP39406, Version 4

## Appendix 5

### Correction Formulas for QTc Intervals

Fridericia's correction for QTc Measurement – QTcF

$$QTcF \text{ (msec)} = \frac{QT \text{ (msec)}}{\sqrt[4]{RR \text{ (msec)} / 1000}}$$

Example: QTcF of a subject with a QT of 386 msec and a RR of 848 msec

$$QT \text{ (msec)} = 386$$

$$RR \text{ (msec)} = 848$$

$$QTcF = \frac{386}{\sqrt[4]{848 / 1000}} = 408 \text{ msec}$$

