**RO7049389—F. Hoffmann-La Roche Ltd**

16/Protocol YP39406, Version 4

---

gastrointestinal symptoms or any other clinically significant illness within two weeks of dose administration.

7. Any confirmed significant allergic reactions (urticaria or anaphylaxis) against any drug, or multiple drug allergies (non-active hay fever is acceptable).
8. Any clinically significant concomitant diseases or condition that could interfere with, or treatment of which might interfere with, the conduct of the study, or that would, in the opinion of the Investigator, pose an unacceptable risk to the subject in this study.
9. Confirmed (based on the average of three separate resting blood pressure measurements, properly measured with well-maintained equipment, after at least 10 minutes rest) systolic BP greater than 140 or less than 90 mmHg, and diastolic BP greater than 90 or less than 50 mmHg at screening.
10. Clinically relevant ECG abnormalities on screening ECG, e.g.,
  - a. QTcF > 450 msec or < 300 msec
  - b. Notable resting bradycardia (HR < 45 bpm), or HR > 90 bpm.
  - c. ECGs with documented machine errors in the interval duration assessments
  - d. Evidence of atrial fibrillation, atrial flutter, complete bundle branch block, Wolf-Parkinson-White Syndrome, or cardiac pacemaker.
11. ECG with QRS and/or T-wave judged to be unfavorable for a consistently accurate QT measurement (e.g., neuromuscular artifact that cannot be readily eliminated, arrhythmias, indistinct QTS onset, low amplitude T-wave, merged T- and U-waves, prominent U-waves).
12. Creatinine clearance (CrCl) ≤ 70 mL/min (using the Cockcroft-Gault formula).
13. Positive test at screening of any of the following: hepatitis A (HAV IgM Ab), hepatitis B (HBsAg), hepatitis C (HCV RNA or HCV Ab) or human immunodeficiency virus 1 and 2 (HIV Ab).
14. Any other clinically significant abnormalities in laboratory test results at screening. In the case of uncertain or questionable results, tests performed during screening may be repeated before randomization to confirm eligibility.
15. Participation in an investigational drug or device study within 90 days prior to screening or more than 4 times per year.
16. Donation or loss of blood over 500 mL within 3 months prior to screening.
17. Positive test for drugs of abuse (including recreational drugs) and/or positive alcohol test at screening or on Day -1.
18. Any suspicion or history of drug and/or alcohol abuse within the last year.

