**RO7049389—F. Hoffmann-La Roche Ltd**

21/Protocol YP39406, Version 4

IND	Investigational New Drug (application)
INR	International normalized ratio
IRB	Institutional Review Board
IUD	Intrauterine device
IV	Intravenous
LDL	Low density lipoproteins
LSLO	Last subject, last observation
LSLV	Last subject, last visit
MAD	Multiple ascending doses
NOAEL	No-observed-adverse-effect level
NUC	Nucleos(t)ide analogue
PD	Pharmacodynamic
PK	Pharmacokinetic
PT	Prothrombin time
Q12h	Twice daily, every 12 hours
Q24h	Once daily, every 24 hours
QD	Once daily
QRS	QRS complex
QT	QT interval
QTc	QT corrected for heart rate
QTcF	QT corrected for heart rate using the Fridericia correction factor
RBC	Red blood cell
RNA	Ribonucleic acid
RR	RR interval
SAD	Single ascending dose
SAE	Serious adverse event
SD	Single dose
SoA	Schedule of assessments
ULN	Upper limit of normal
V	Volume
WBC	White blood cell

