#### **4.5.1.4 Electrocardiograms**

##### **12-Lead ECG**

ECGs will be collected after the study subject has been in a supine position for at least 10 minutes. At the specified time-points, 12-lead ECGs will be obtained in triplicate, i.e., three consecutive interpretable 12-lead ECGs within a 2-5-minute interval, and recorded in CRF. Triplicate recordings should be taken for any unscheduled ECG.

All ECG recordings must be performed using a standard digital high-quality, high-fidelity ECG machine equipped with computer-based interval measurements. Automated ECG intervals (PR [PQ], QRS, QT, QTcF [to be derived in eCRF]) and HR will be captured, or calculated, and the changes in T-wave and U-wave morphology will be documented.

T-wave information will be captured as normal or abnormal, U-wave information will be captured in two categories: absent/normal or abnormal.

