#### **6.5.4      ECG Data Analysis**

ECG data will be presented by individual listings with flagging of values outside the normal ranges and flagging of marked abnormalities. In addition, tabular summaries will be used, as appropriate.

Summary descriptive statistics for the actual values and changes from baseline will be tabulated by nominal time for HR, QRS duration, PR and QTcF (see [Appendix 5](#)). For multiple measurements taken at a nominal time-point, the average of these measurements will be used as the value at that nominal time-point in all summaries. In addition, QTcF will be categorized at each time-point as  $\leq 450$  msec,  $> 450-480$  msec,  $> 480-500$  msec and  $> 500$  msec and summarized. Similarly, a summary will be provided of the QTcF changes from baseline at each time-point categorized as  $< 30$  msec, 30-60 msec, and  $> 60$  msec. Changes of the overall ECG interpretation, T-wave and U-wave morphology will be summarized.

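### Does Appendix 5 correct QT with a fourth root, so that QTcF is misread at the trial's thresholds?

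*Combined protocol and SAP*

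**What the plan says.** Appendix 5 is headed "Fridericia's correction for QTc Measurement" and holds two expressions, a general formula and a numerical case: "Example: QTcF of a subject with a QT of 386 msec and a RR of 848 msec". In the text version, both expressions carry a root index of 4, and the case ends "QTcF = \frac{386}{\sqrt[4]{848 / 1000}} = 408" msec.

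The List of Abbreviations defines QTcF by name only: "QT corrected for heart rate using the Fridericia correction factor". No exponent is stated in words anywhere.

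QTcF is used in these places:

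- **Derivation.** Section 4.5.1.4 lists it among the captured intervals as "QTcF [to be derived in eCRF".
- **Eligibility.** Exclusion criterion 10 (Synopsis and Section 4.1.3) names "QTcF > 450 msec or < 300 msec" as an example, next to "Notable resting bradycardia (HR < 45 bpm), or HR > 90 bpm".
- **Dose escalation.** Section 3.1.2.1 gives QTcF above 500 msec, or more than 60 msec over the pre-dose baseline, as an example of an ECG change that counts.
- **Analysis.** Section 6.5.4 refers to Appendix 5 and sorts the values into bands ("In addition, QTcF will be categorized at each time-point as" and so on), with cuts at 450, 480 and 500 msec and, for change from baseline, at 30 and 60 msec.

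**The concern.** Read literally, the appendix contradicts itself: the expression shown does not give the answer beside it. This is also the only place where the correction is written out. Section 6.5.4 points to it, and someone has to program the eCRF derivation, so it is natural to fear that the wrong exponent was carried into the data.

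Safety is the primary objective, and the error would not be a constant shift. A fourth root corrects too little, so QTcF would be too low at rates above 60 bpm and too high below 60 bpm. Subjects near 450 msec could be wrongly admitted or excluded, depending on heart rate. High values could fall into a lower band of the ECG tables. A drug effect on heart rate would leak into the QTcF change from baseline.

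**Working it through.** **Inputs.** QT = 386 msec, RR = 848 msec and stated answer 408 msec, all from Appendix 5. The formula is QTcF = QT / (RR/1000)^(1/k), where k is the root index.

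**Step 1: reproduce the stated figure.**

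| k | 0.848^(1/k) | 386 / 0.848^(1/k) | Gives 408? |
|---|---|---|---|
| 2 | 0.9209 | 419.2 | no |
| 3 | 0.9465 | 407.8 | yes, after rounding |
| 4 | 0.9596 | 402.2 | no |

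**Step 2: ask which exponent the answer implies.** Solving for the exponent gives ln(408/386) / (−ln 0.848) = 0.336. A printed 408 can stand for anything from 407.5 to 408.5, so the exponent lies between 0.329 and 0.344. That interval contains 1/3 and excludes 1/4. Whoever calculated the example used a cube root.

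**Step 3: weigh the evidence on the index.** Four items bear on it:

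- The name of the correction fits a cube root.
- The two inputs taken with the answer fit a cube root, by Steps 1 and 2.
- The List of Abbreviations again gives the Fridericia name.
- The root index, as transcribed, says 4.

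Only the last item disagrees. It is one tiny character in a formula that a program rebuilt from a PDF page. The same text version replaces blacked-out material in Section 1.2.1 with a prose description of black bars, which is plainly not the sponsor's wording. Fine detail in this transcription cannot be relied on by itself.

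**Step 4: size the effect if a fourth root had been programmed.** The ratio of the fourth-root to the cube-root value is r^(1/3 − 1/4) = r^(1/12), with r = RR in seconds = 60/HR.

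| HR (bpm) | r | Cube-root 450 would read | Cube-root 500 would read |
|---|---|---|---|
| 45 | 1.333 | 460.9 | 512.1 |
| 60 | 1.000 | 450.0 | 500.0 |
| 75 | 0.800 | 441.7 | 490.8 |
| 90 | 0.667 | 435.0 | 483.4 |

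The range 45 to 90 bpm is the one admitted at screening. For change from baseline, take as an assumption 400 msec at 60 bpm rising to 461 msec at 90 bpm. The cube-root change is +61 msec. The fourth-root change is 445.7 − 400 = +45.7 msec. These are worthwhile differences, but they arise only if a fourth root was actually programmed.

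**Step 5: look for any sign that it was.** Section 4.5.1.4 says where QTcF is derived, not by what algorithm. No section describes an eCRF calculation with a fourth root. The worked example serves as a test case: code with index 4 returns 402, not 408, and the mismatch is visible at once.

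**The case for a change.** The best argument for the concern is that the index is 4 in both expressions, that the rest of the appendix reads cleanly, and that the document gives no other explicit formula. On that view, the text as it stands is the definition, and a programmer could follow it.

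The arithmetic in this argument stands: index 4 does not give 408. The inference from it does not.

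- Two appearances of the same small glyph, on one page and read by the same program, are not independent evidence. One misreading explains both.
- A clash between the index and the stated answer is exactly what a misread 3 would produce.
- The definition does not rest on the index alone. The protocol names the correction twice and supplies a numerical answer that fixes the exponent.

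The feared consequences are also less direct than they seem. The immediate repeat-ECG trigger in Section 4.5.1.4 uses the QTc reported by the machine, not the appendix formula. In Section 3.1.2.1, QTcF is an illustration within a rule that needs more than two subjects on active drug with related, clinically significant changes of the same kind. Exclusion criterion 10 likewise lists QTcF as an example. Section 6 makes all analyses descriptive, so no test depends on the 450 or 500 msec cut.

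What remains is that a glance at the original page would settle the index. That is a check on the transcription and changes no result in the plan.

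**Conclusion.** The concern does not hold. The stated 408 msec follows from the named correction with a cube root (407.8), and the exponent implied by the example, 0.329 to 0.344, rules out a fourth root. The 4 is most plausibly a 3 misread from the PDF. The 5.6 msec gap in the example, and the shifts of −15.0 msec at 90 bpm and +10.9 msec at 45 bpm around the 450 msec limit, belong to a formula that nothing in the protocol shows to be in use.

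This conclusion assumes that the original page carries a cube root, which the text version cannot prove. If the page did show a 4, it would be a typographical slip contradicted by the heading and the answer beside it. The threshold effects would still need a further assumption: that the eCRF was programmed from the slip and never tested against the 408 msec example.

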**RO7049389—F. Hoffmann-La Roche Ltd**  
81/Protocol YP39406, Version 4

## Appendix 6

### Cockcroft Gault Equation for Calculation CrCl

The Cockcroft-Gault equation will be used to calculate creatinine clearance (CrCl) (Conventional units = mL/min or SI units = mL/sec). Baseline body weight (ABW) will be used for calculation of CrCl.

Conventional Units:

$$\text{Males (mL/min)} = \frac{(140 - \text{Age}) * \text{ABW (kg)}}{72 * \text{Serum Creatinine (mg/dL)}}$$

*Females (mL/min)* = Male value x 0.85

Conversion Factor for Creatinine Clearance:

- SI Units (mL/sec) = Conventional units (mL/min)  $\times$  0.0167
- Conventional Units (mL/min) = SI Units (mL/sec) / 0.0167

Conversion Factor for Serum Creatinine:

- Conventional units (mg/dL) = SI units ( $\mu\text{mol/L}$ ) / 88.4
- SI Units ( $\mu\text{mol/L}$ ) = Conventional Units  $\times$  88.4

**RO7049389—F. Hoffmann-La Roche Ltd**  
82/Protocol YP39406, Version 4
